5.1. Hypotheses and Decision Rules

PF-04965842 200 mg QD will be declared superior to placebo if the null hypothesis of no difference between PF-04965842 200 mg QD versus placebo for **both** co-primary endpoints is rejected at the 5% significance level. Similarly, PF-04965842 100 mg QD will be declared superior to placebo if the null hypothesis of no difference between PF-04965842 100 mg QD versus placebo for **both** co-primary endpoints is rejected at the significance level specified below.

[figure not shown]
A sequential Bonferroni-based iterative multiple testing procedure to strongly control the familywise Type 1 error at 5% will be used for testing each of the two PF-04965842 doses (200 mg QD and 100 mg QD) versus placebo on the primary and key secondary endpoints. The procedure belongs to a class of consonant multiple test procedures ([Hommel et al. 2007](#)) which are a subclass of the closed test procedures ([Marcus et al. 1976](#)).

The procedure will first test the Week 12 co-primary endpoints (IGA and EASI-75) for 200 mg QD vs placebo at a 5% significant level. If this hypothesis is not rejected, then no further testing will be conducted. If this hypothesis is rejected, then testing may continue on

two paths depending on the testing for Week 2 NRS4 for severity for 200 mg QD vs placebo at a 2.5% significance level:

- If the hypothesis for the Week 2 NRS4 for severity for 200 mg QD vs placebo is rejected, then the unused alpha level of 2.5% will be passed on to a series of testing in Sequence A (see Figure 2 below) at a 5% significance level. If any hypothesis in this sequence is not rejected, then the procedure stops.
- If the hypothesis for the Week 2 NRS4 for severity for 200 mg QD vs placebo is not rejected, then the series of testing in Sequence A (see Figure 2 below) will be tested at a 2.5% significance level. If any hypothesis in this sequence is not rejected, then the procedure stops. If all hypotheses in this sequence are rejected, then the unused alpha level of 2.5% will be passed on to the testing of hypotheses for Week 2 NRS4 for severity (200 mg QD vs placebo) at a 5% significance level.

Figure 2 Schematic for Multiple Testing Procedure

Hypotheses for all other endpoints not described here are to be tested at the nominal 5% significant level, without making adjustments for multiple comparisons.

090177e1912f28b6\Approved\Approved On: 26-Jun-2019 09:22 (GMT)

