5.2.1. Analyses of Binary Data

Binary data at each scheduled visit will be analyzed by two approaches: (1) the test of hypothesis (and the p-value) between the PF-04965842 treatment groups versus the placebo group will be conducted by the Cochran-Mantel-Haenszel (CMH) statistic adjusting for the effect of randomization strata; p-values from the CMH statistic will be used to establish the superiority of each dose of PF-04965842 to placebo in binary responses; and (2) the proportion of responders in the PF-04965842 treatment groups versus the placebo group will be summarized by the difference and its 95% confidence interval obtained by normal approximation. The difference in proportions will be calculated within each randomization stratum. The final estimate of the difference in proportions will be a weighted average of these stratum-specific estimates using CMH weights. The CMH weight w_k for stratum k ($k = 1, 2, 3, 4$) is given by,

$$w_k = \frac{\frac{n_{ik} n_{ck}}{n_{ik} + n_{ck}}}{\sum_{j=1}^4 \frac{n_{ij} n_{cj}}{n_{ij} + n_{cj}}}$$

where n refers to sample size, the subscript c refers to a comparator group (e.g., placebo) and the subscript i refers to a test group (e.g., either the low or high doses; so that two test statistics are calculated, one for each dose versus placebo). The difference is estimated as $\hat{d} = \sum_{k=1}^4 w_k (\hat{p}_{ik} - \hat{p}_{ck})$, where \hat{p} refers to the estimated relative frequency. An estimate for \hat{p} is obtained as x/n , where x is the number of responders.

Two-sided 95% confidence intervals for the difference (based on a normal approximation) are formed by:

$$\hat{d} \pm 1.96 \sqrt{\sum_{k=1}^4 w_k^2 \left(\frac{\hat{p}_{ik}(1 - \hat{p}_{ik})}{n_{ik}} + \frac{\hat{p}_{ck}(1 - \hat{p}_{ck})}{n_{ck}} \right)}$$

In the above formula for the variance of \hat{d} (under the square-root sign), when the number of responders is zero ($x = 0$), then \hat{p} will be replaced by $0.5/(n + 1)$. This change will be made only for calculating the variance of \hat{d} and not anywhere else. Estimates of the difference in proportions along with the two-sided 95% confidence interval will also be provided for the PF-04965842 200 mg QD group versus the PF-04965842 100 mg QD group. No hypotheses will be tested.

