This imputation will be repeated multiple times with different MCMC samples to obtain multiple completed datasets. For each such completed dataset, the estimates of the proportions and CMH-weighted difference of proportions between each PF-04965842 dose group and placebo will be obtained along with the associated standard errors using the methods in [Section 5.2.1](#). Rubin’s rule (Rubin, 1987) will be used to combine the multiple estimates and standard errors across the imputed datasets and provide p-values.

The above analysis can be repeated for different combinations of MNAR quantities which will be applied to the probability of response to assess when the conclusion might change (i.e., tipping). Two important scenarios are included in the tipping point analysis framework. When the MNAR quantities are zero and the posterior predictive probabilities in the PF-04965842 dose groups are not shifted, results are obtained under an assumption of MAR for the missing data mechanism. Alternatively, at the other extreme, when the MNAR quantities are 1.0 for each PF-04965842 dose group, results are obtained under an assumption that the distribution of the missing responses after discontinuation of either dose of PF-04965842 is the same as that of the missing responses on the placebo arm. More detailed descriptions are provided in [Appendix 3](#).

Due to a technical error in the process of transmission and collection of electronic data with the device, the data on the pruritus NRS scale was not collected from several subjects at the scheduled visits of Week 2 (Day 15) and after. This was not restricted to a particular site or country and was not indicative of being related to the missing value of pruritus endpoint or any other endpoints. As such, the missing data mechanism may be reasonably assumed to be missing completely at random or missing at random.

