For the binary endpoints derived from the pruritus NRS, a hybrid approach will be used which is partially based on the multiple imputation method described in the previous paragraph. For this analysis, all data missing due to dropouts will be defined as “non-responsive” as described in the first paragraph, but any other data which remains missing at any intermittent visits will be handled using multiple imputation under the MAR assumption (which may be obtained by substituting the MNAR quantities as zero in the analysis described in the previous paragraph; see also, [Appendix 3](#)). At any particular visit, if there are 5 or fewer subjects with missing data in each treatment group after applying the non-responder definition, no imputations will be performed, and the data will remain missing. Note that, as described in the previous paragraphs, the GLMM will be fit to the observed data (i.e., without defining missing data due to dropout as “non-response”).

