6.3. Key Secondary Endpoints

6.3.1. Weeks 2, 4 and 12 NRS4 for severity Response

- Summary: Proportion of subjects with NRS4 for severity response at Weeks 2, 4 and 12;
- Population: Subjects from the (FAS, PPAS) with a baseline NRS score for severity ≥ 4 ;
- Statistical Method: CMH and normal approximation in [Section 5.2.1](#). Visit windows will be used as described in [Appendix 2](#);
- Missing Data: Two analyses will be performed:
 - Primary Analysis: Missing data arising due to subject dropout are considered “non-response”. For any other missing observations, a multiple imputation

approach based on a GLMM will be used. (see the last two paragraphs within [Section 5.3.1](#)). This analysis will be based on both the FAS and the PPAS.

- Sensitivity Analysis: All missing data will be considered as “non-response”. This analysis will be based on the FAS only.

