$$\begin{aligned} \pi_{i,3,4}^{*b} &= \pi_{i,3,4}^b, \\ \pi_{i,1,4}^{*b} &= \delta_1 \pi_{i,3,4}^b + (1 - \delta_1) \pi_{i,1,4}^b, \\ \pi_{i,2,4}^{*b} &= \delta_2 \pi_{i,3,4}^b + (1 - \delta_2) \pi_{i,2,4}^b \end{aligned}$$

We then sample the single imputed value $\widetilde{Y}_{i,j}^b$ from a Bernoulli distribution with probability of success $\pi_{i,T_i,4}^{*b}$. For the present analysis, the responses from the placebo arm are not shifted.

Analysis of an imputed data set will produce an estimate as well as standard error of the treatment difference using CMH and normal approximation in [Section 5.2.1](#). For a given value of MNAR parameter δ , this is repeated for B (typically, $B=500$) times to generate B complete imputed data sets and these B sets of estimates are combined using the Rubin's

Method (Rubin, 1987). This can then be repeated for different values of MNAR parameter δ to evaluate the impact of missing data. Note that $\delta = (0, 0)'$ corresponds to an MAR analysis and $\delta = (1, 1)'$ corresponds to an analysis commonly known as Jump-To-Reference (JTR). As a special case, we will consider $\delta_1 = \delta_2$ for our analyses.

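### When NRS4 is multiply imputed, the only p-value rule the SAP writes is an unpooled Wald test, which conflicts with the named CMH test and runs slightly above its level at 2:1 allocation

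*SAP*

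**What the plan says.** SAP 5.2.1 sets the general rule for binary endpoints: "p-values from the CMH statistic will be used to establish the superiority of each dose of PF-04965842 to placebo in binary responses". The same section gives a CMH-weighted difference in proportions with a 95% interval built on separate (unpooled) variances in each arm and stratum. SAP 6.3.1 and Appendix 1 list CMH for NRS4.

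SAP 5.3.1 reports a device error: "the data on the pruritus NRS scale was not collected from several subjects at the scheduled visits of Week 2 (Day 15) and after". For NRS4, dropouts therefore count as non-responders, and 6.3.1 continues: "For any other missing observations, a multiple imputation" approach based on the GLMM is used. SAP 5.3.1 calls this arrangement "a hybrid approach will be used which is partially based on the multiple imputation method described in the previous paragraph". There is a per-visit threshold: "if there are 5 or fewer subjects with missing data in each treatment group after applying the non-responder definition, no imputations will be performed". More than 5 missing in any one of the three groups therefore triggers imputation for the whole visit.

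The imputation method referred to takes the CMH-weighted difference and its standard error from each completed data set. Rubin's rule "will be used to combine the multiple estimates and standard errors across the imputed datasets and provide p-values". Appendix 3 repeats this: "Analysis of an imputed data set will produce an estimate as well as standard error of the treatment difference using CMH and normal approximation". Neither place says how to combine the CMH statistic itself over imputations.

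NRS4 at Weeks 2, 4 and 12 belongs to the family for which SAP 5.1 and Protocol 9.2.2 claim strong control at 5%. Week 2 NRS4 at 200 mg starts at 2.5%. If it is rejected, its alpha is "passed on to a series of testing in Sequence A (see Figure 2 below) at a 5% significance level". If it is not, Sequence A runs at 2.5%, and Week 2 NRS4 can be retested at 5% once all of Sequence A is rejected.

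**The concern.** A programmer who has imputed data cannot obtain the named CMH p-value from this SAP. The one p-value rule available gives a different test. The two differ in variance: CMH uses a variance computed under the null, with both arms combined, while the 5.2.1 interval uses each arm's own observed rate. The placebo group is half the size of each drug group. A chance-low placebo count therefore widens the difference and at the same time shrinks the unpooled standard error, so the Wald statistic leans towards the drug.

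At stake is a set of key secondary claims inside a controlled family. Where every hypothesis tested earlier is false and rejected, the familywise error equals the size of the first true-null NRS4 test.

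**Working it through.** **Inputs from the documents.** 150/150/75 subjects and four strata (SAP 2.2); CMH weights, unpooled variance and the 0.5/(n+1) zero-cell rule (SAP 5.2.1); Rubin's rule (SAP 5.3.1, Appendix 3). Significance levels are taken as two-sided.

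**Assumptions.** The documents give no NRS4 rate, stratum mix or missing count. Assumed: strata of 72/48/18/12 (drug) and 36/24/9/6 (placebo), data missing completely at random, and the null rates and missing fractions shown.

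**Plan's own figures.** The SAP gives no operating figure for NRS4, so its co-primary power is reproduced first, for 150 v 75 at 5% two-sided.
- IGA, 6% v 26%: null SE 0.0558, alternative SE 0.0451, power = Φ((0.20 − 1.96×0.0558)/0.0451) = 97.8%.
- EASI-75, 15% v 45%: Φ((0.30 − 1.96×0.0675)/0.0579) = 99.8%.
- Both agree with the stated minima of 95% and 99%, and 0.95×0.99 = 94.05% matches the stated joint 94%.

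**The two tests.** In each stratum let n_i and n_c be the arm sizes, N their sum, m the total responders, h = n_i·n_c/N and w = h/Σh. Both tests use d = Σw(p_i − p_c).
- CMH variance: V0 = Σ[n_i·n_c·m(N−m)/(N²(N−1))]/(Σh)². Then d/√V0 is the CMH statistic without continuity correction.
- Wald variance: V1 = Σw²[p_i(1−p_i)/n_i + p_c(1−p_c)/n_c].
- After imputation: T = U + (1+1/B)·(between-imputation variance), where U is the mean of V0 or V1 over B imputations.

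**Worked example** (responders by stratum 13/9/3/2 v 3/2/1/0; per-arm imputation).
- 5 missing in each group, 27/145 v 6/70, nothing imputed. d = 0.1003. CMH: 0.1003/0.0529 = 1.90, p = 0.058. Wald on the same table: 0.1003/0.0473 = 2.12, p = 0.034.
- One more drug-arm non-responder missing, 27/144 v 6/70, imputation triggered. d = 0.1015, between-imputation variance 0.00012. Wald: U = 0.00212, SE 0.0473, p = 0.032. CMH null variance: U = 0.00264, SE 0.0526, p = 0.054.
- 15 and 8 missing: 26/135 v 6/67 gives 0.038 (Wald) v 0.059; 28/135 v 6/67 gives 0.019 v 0.035, which splits at 2.5% only.

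Almost all of the move from 0.058 to 0.032 is the change of variance, since Wald gives 0.034 before anything is imputed.

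**Size by simulation** (per-arm imputation, 60,000 replicates, 40 imputations; missing 8/4, 15/8 or 22/11, that is, about 5-15%).

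| | Wald, Rubin | CMH null variance, Rubin |
|---|---|---|
| Two-sided, level 5%, null 10-30% | 5.2-5.8% | 4.8-5.0% |
| Drug-favouring tail (even split 2.5%) | 3.1-3.5% | 2.2-2.5% |
| Two-sided, level 2.5%, null 10-30% | 2.7-3.0% | 2.3-2.5% |
| Drug-favouring tail (even split 1.25%) | 1.7-2.0% | 0.9-1.3% |
| Two-sided, null 6-8%, levels 5% / 2.5% | 4.0-4.9% / 1.9-2.5% | not needed here |

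A fresh run of the same design agreed to within about 0.1 percentage point.

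**With the Appendix 3 model** (10% missing, null 10/20%, assumed random-intercept SD 2): Wald two-sided 5.3/5.5% and 2.8/2.9% at the two levels; CMH null variance 4.9/4.8% and 2.4/2.2%.

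**Without imputation** (exact, one 150 v 75 table, 5% level, null 10/15/25/40%): Wald drug tail 4.1/3.7/3.2/2.9% against CMH 1.9/2.3/2.3/2.4%. The Wald total is 5.3-5.9%. The lean is present with complete data.

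**How often the tests disagree under a true benefit** (5% level, 10% missing): only Wald rejects in 5.3-7.7% of trials for 10 v 20-25% or 15 v 25-30%, in 1.1% for 6 v 26%, and in 0.1% for 15 v 45%. Only CMH rejects in 0.00%.

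**The case against.** The strongest reply is that CMH remains the named test in three places. The Rubin sentence sits in text on additional analyses and reaches NRS4 only through a method described as partial. That stands: the SAP does not announce a Wald test for NRS4. The firm defect is a gap and a conflict, with the only written route leading to Wald.

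Second, a reader might infer that the 5-or-fewer threshold itself inflates error. The documents do not support that. The threshold is prespecified and depends on missing counts alone; under missingness unrelated to outcome it carries no outcome information. It decides which test applies, but the excess is the Wald variance.

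Third, a reader might count the Wald-only rejections as false claims. They occur under a true benefit and are correct rejections; they show only that a borderline decision depends on the test. Part of the tail gap is also CMH falling below an even split.

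Fourth, 6.3.1 already has a CMH analysis with all missing data as non-response. It is a sensitivity analysis and does not decide the hypothesis.

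Fifth, whether imputation is triggered is unknown. It is least likely at Week 2, where the diary is daily to Day 15 and the window covers Days 2-22. It is likelier at Weeks 4 and 12, when the scale is completed only on visit days. The place of those tests within Sequence A is shown only in Figure 2, which was not available here, so the familywise case above is a worst case.

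**Conclusion.** The point holds as a modest one. If NRS4 is imputed and the written rule is followed, a key secondary test conflicts with the named CMH test and runs about 0.2-0.8 points above a 5% level (5.2-5.8%) and 0.2-0.5 above 2.5% (2.7-3.0%), with the excess favouring the drug. This rests on null rates of 10-30%, 5-15% missing at random and the assumed strata. At null rates of 6-8% there is no excess in total size. If NRS4 effects are as large as those planned for the co-primary endpoints, the choice of test changes the decision in about 1% of trials or fewer. The primary analyses of IGA and EASI-75 are not touched, because they use CMH without imputation.

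**What to change.** In SAP 5.3.1 and 6.3.1, name one post-imputation decision p-value for NRS4 that reduces to the 5.2.1 CMH test when nothing is imputed. One option is Rubin's rule on the weighted difference with V0 above as the within-imputation variance. Another stated pooling of the CMH statistic would serve equally well. Keep the unpooled standard error for the 95% interval only.

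The cost is a few lines of SAP text and code. The p-value becomes slightly less favourable to the drug. In borderline data it may disagree with the interval, as can already happen with complete data under 5.2.1.

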5.3.2. Continuous Endpoints

For non-PRO continuous endpoints measured longitudinally, missing values post-baseline will not be imputed explicitly. For such endpoints, assuming that the missing data mechanism is missing at random (MAR), the data will be analyzed based on a restricted maximum likelihood (REML) using a linear mixed-effect model with repeated measures for these continuous variables (see [Section 5.2.3](#)). This model will yield valid inferences in the presence of a missing data mechanism that is MAR.

090177e1912f28b6\Approved\Approved On: 26-Jun-2019 09:22 (GMT)

For the continuous PRO variables such as pruritus NRS, DLQI / CDLQI, POEM, PSAAD, HADS, EQ-5D-5L / EQ-5D-Y, SF-36v2 and FACIT-F, rules suggested by the developers of these instruments will be followed in calculating the missing values. If these rules are not enough for imputing a value, then the missing values will be handled in the same way as non-PRO variables.

5.3.3. Time to Event Endpoints

For time-to-event endpoints, subjects who complete the study without the event of interest or those who withdraw before experiencing the event of interest will have their event times right censored at the last available measurement time (or visit) used to define whether the subject experienced the associated event (ie, the event of interest is presumed to have occurred beyond this time point).

6. ANALYSES AND SUMMARIES

Analysis will be done pairwise between each of the PF-04965842 QD treated groups (200 mg and 100 mg) and placebo (two separate tests of hypotheses). An analysis with point estimates of the difference and the associated 95% confidence intervals will also be done for PF-04965842 200 mg QD versus PF-04965842 100 mg QD without testing any hypotheses.

A summary of analyses for clinical efficacy endpoints is provided in [Appendix 1](#). Visit windows to be used for all efficacy analyses and some relevant safety analyses are detailed in [Appendix 2](#).

Data collected at Week 16 will be displayed in listings only, and will not be part of any analyses, unless specifically noted otherwise.

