1.2.4. Phase 2b in AD (B7451006)

B7451006 was a Phase 2b proof-of-concept trial in adults (ages 18-75) with AD investigating doses of 10, 30, 100, and 200 mg PF-04965842 or placebo taken once daily (QD) for up to 12 weeks. The primary endpoint in this study was the proportion of subjects achieving an IGA score of clear (0), or almost clear (1), and a ≥ 2 -point improvement from baseline at Week 12. The baseline was defined as the IGA score on Day 1 pre-dose.

At Week 12, IGA response rates of PF-04965842 100 mg and 200 mg dose groups were significantly greater than placebo in patients with moderate to severe AD. The IGA response rates of the 200 mg and 100 mg groups were 44.5% and 27.8%, compared to 6.3% in the placebo group, ($P= 0.0032$ and 0.0184 , respectively). The percent change from baseline (% CFB) in EASI scores at Week 12 were significantly higher for both the 200 mg and 100 mg groups compared to placebo ($P<0.0001$ and $P=0.0091$, respectively). PF-04965842 demonstrated a rapid onset of action. In the 200 mg group, IGA and EASI scores improved until week 4 and week 6, respectively, and maintained their effect through 12 weeks of treatment. Response rates at Week 12 for the 10 mg and 30 mg groups were not significantly different from placebo. A key differentiating feature for the JAK1 inhibitor is rapid resolution of itch associated with AD. Significant separation from placebo was achieved for the pruritus NRS score as early as 2 days after initiation of treatment for the 200 mg dose group.

Overall, the results demonstrated dose-dependent increases in responses at Week 12 for key efficacy endpoints (IGA, EASI and pruritus NRS score).

PF-04965842 appeared generally safe and well tolerated in this study. AEs and SAEs were numerically higher in subjects receiving PF-04965842 compared to placebo, but did not appear to increase with dose. The most common AEs were in the infections and infestations, skin and subcutaneous tissue disorders and gastrointestinal disorders system organ class (SOC), and the majority of the AEs were mild. There were 2 cases of herpes zoster, one in the 10 mg group (not treatment related), and one in the 30 mg group (treatment related). There were dose-dependent decreases in platelet counts observed in the study, which plateaued at Week 4, and were not generally clinically relevant. Further details of the clinical Phase 2 development program can be found in the Investigator's Brochure (IB).

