6.3. Follow-up Visits

6.3.1. Visit 9, Day 120/Week 16 (± 3 day)

- Administer PROs including PtGA, DLQI (or CDLQI), POEM, HADS, EQ-5D-5L (or EQ-5D-Y), SF-36v2, Acute and FACIT-F (or Peds-FACIT-F). SF-36v2 will be completed by adult subjects only;
- Adolescents 12-17 years of age will not complete the SF-36v2. Adolescents 12-17 years of age will complete the CDLQI instead of the DLQI, the EQ-5D-Y instead of the EQ-5D-5L and Peds-FACIT-F instead of the FACIT-F;
- Review PSAAD daily completion (in selected countries) and pruritus NRS completion for this visit in the eDiary;
- Obtain vital signs including pulse rate, sitting blood pressure, respiratory rate and oral or tympanic temperature (after at least 5 minutes of rest);

- Perform a single 12-lead electrocardiogram (ECG);
- Conduct targeted physical examination;
- Obtain fasting samples for laboratory testing: serum chemistry, hematology (including coagulation panel), lipid profile, and urinalysis;
- Urine pregnancy test (female subjects of childbearing potential, including adolescents aged 12 years and older, regardless of whether they have experienced menarche);
- Conduct clinical evaluations including IGA, SCORAD, EASI and BSA (calculated in the EASI);
- Assess need for contraception and adherence to applicable lifestyle requirements (Section 4.4). Establish willingness and ability to comply with lifestyle requirements going forward in the study;
- Review any changes in the subject's concomitant medications and treatments information;
- Assess and record any Adverse Events since the last visit.

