3.5.1. Adverse Events

An adverse event will be considered a Treatment-Emergent Adverse Event (TEAE) if the event started during the effective duration of treatment. All events that start on or after the first dosing day and time / start time, if collected, but before the last dose plus the lag time (28 days) will be flagged as TEAEs. The algorithm will not consider any events that started prior to the first dose date.

A 3-tier approach will be used to summarize AEs. Under this approach, AEs are classified into one of 3 tiers. Different analyses will be performed for different tiers (See [Section 6.9.1](#)).

Tier-1 events: These are pre-specified events of clinical importance and are maintained in a list in the product's Safety Review Plan. Herpes zoster and serious infections have been identified as Tier-1 events. No other Tier-1 events have been identified so far and the study team will continue monitoring all safety events.

Tier-2 events: These are events that are not Tier-1 but are "common". A MedDRA Preferred Term (PT) is defined as a Tier-2 event if there are at least 4 subjects with an event in any treatment group.

Tier-3 events: These are events that are neither Tier-1 nor Tier-2 events.

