6.9. Safety Summaries and Analyses

Safety analyses will be based on the SAF analysis set.

All clinical AEs, SAEs, TEAEs, withdrawal due to AEs, ECGs, vital signs and safety laboratory data will be reviewed and summarized on an ongoing basis during the study to evaluate the safety of subjects.

Safety data will be presented in tabular and/or graphical format and summarized descriptively, where appropriate. All safety endpoints will be listed and summarized in accordance with CaPS. Categorical outcomes (e.g., AEs) will be summarized by subject counts and percentage. Continuous outcome (e.g., blood pressure, pulse rate, etc.) will be summarized using N, mean, median, standard deviation, etc. Change from baseline in laboratory data, ECGs and vital signs will also be summarized. Subject listings will be produced for these safety endpoints accordingly.

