6.9.2. Laboratory Data

Laboratory data will be listed and summarized in accordance with the CaPS reporting standards. Summaries of subjects meeting pre-specified monitoring and discontinuation criteria will be created using methods for categorical data (see [Section 5.2.4](#)).

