Appendix 2. Definition and Use of Visit Windows in Reporting

Visit windows will be used for efficacy variables, and for any safety data that display or summarize by study visit. For other endpoints (e.g., ECG, vital signs), visit windows will be applied for summary statistics by study visits if required.

Visit Label	Target Day	Definition [Day window]
Screening		Days -28 to Day -1
Baseline	Day 1 (Day of first dose)	Last observation prior to and including day of first dose
Week 2	15	Days 2 to 22
Week 4	29	Days 23 to 43
Week 8	57	Days 44 to 71
Week 12	85	Days 72 to 99
Follow Up/End of Study		
Week 16	-	Days 100 to -

For the lab values, if the calculated study day for the labelled baseline visit is not study Day 1, but falls within 28 days before the start of the study dosing, then that data should be used for the baseline instead of leaving baseline missing.

For the other values, if the calculated study day for the labelled baseline visit is not study Day 1, but falls before the start of the study dosing, then that data should be used for the baseline instead of leaving baseline missing.

If two or more visits fall into the same window, keep the one closest to the Target Day. If two visits are equaled distant from the Target Day in absolute value, the later visit should be used.

Safety analysis may follow CaPS standards.

090177e1912f28b6\Approved\Approved On: 26-Jun-2019 09:22 (GMT)

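### By default the SAP specifies no by-arm summary of off-drug laboratory, vital-sign and ECG values from the follow-up visit, and its day windows can place some of them among on-treatment results

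*SAP*

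**What the plan says.** **The default.** SAP Section 6, before any endpoint is discussed: "Data collected at Week 16 will be displayed in listings only, and will not be part of any analyses, unless specifically noted otherwise". The preceding sentence concerns visit windows for efficacy and for some safety analyses, so the rule is not confined to efficacy. Section 6.9 (safety) sits beneath it.

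**What is collected.** Protocol 6.3.1 requires at Visit 9: "Obtain fasting samples for laboratory testing: serum chemistry, hematology (including coagulation panel), lipid profile, and urinalysis". Vital signs and a 12-lead ECG are also taken. The visit is for subjects who stop early and for completers who do not enter the extension study.

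**What is planned for these data.**
- SAP 6.9: "Change from baseline in laboratory data, ECGs and vital signs will also be summarized". No visits are named.
- SAP 6.9.2: "Laboratory data will be listed and summarized in accordance with the CaPS reporting standards". It adds: "Summaries of subjects meeting pre-specified monitoring and discontinuation criteria will be created using methods for categorical data". Again no visits are named and no time limit is given.
- SAP 6.9.3 lists vital signs to Week 12/End of Treatment. SAP 6.9.4 lists ECG at baseline and End of Treatment.
- SAP 6.9.5 takes physical examinations at every available post-baseline visit.
- SAP Appendix 2: "Visit windows will be used for efficacy variables, and for any safety data that display or summarize by study visit". Its table has a Week 16 row starting at Day 100, and it ends by permitting safety analysis to follow the sponsor's CaPS standards.
- SAP 3.5.1, on the end of the adverse-event window: "but before the last dose plus the lag time (28 days) will be flagged as TEAEs".

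**The known effect.** Protocol 1.2.4: "There were dose-dependent decreases in platelet counts observed in the study". Protocol 1.4 lists reduced platelet count among the potential risks, and Protocol 1.5 says a dose-response was evident for platelets alone.

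**The concern.** Visit 9 is the only scheduled visit at which subjects are off drug, so it is where the trial can show whether platelet counts recover, stay low or overshoot after stopping. The protocol itself cares about this: Section 6.4 has clinically significant laboratory abnormalities followed until they normalise, return to baseline or stabilise. The SAP plans no matching summary.

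The exception clause in Section 6 could have supplied one, but the laboratory, vital-sign and ECG sections do not use it. The wording for physical examinations shows that broader scope was written where it was wanted.

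A second problem lies in Appendix 2, which assigns values by study day and not by time since last dose. Off-drug values from early discontinuers can then stand in a by-visit table as though they were on-treatment values. If counts are recovering, that would tend to dilute a drug effect.

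**Working it through.** No stated figure is at issue, so the check is day arithmetic on the plan's own windows.

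**Inputs.** Visit 9 is 4 weeks (28 days) after End of Treatment or early termination, ±3 days (Schedule of Activities). The SAP Appendix 2 windows are Week 2 = Days 2 to 22, Week 4 = Days 23 to 43, Week 8 = Days 44 to 71, Week 12 = Days 72 to 99, Week 16 = Day 100 onward. Dosing runs to Day 85.

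**Step 1: where Visit 9 lands.** Visit 9 day = End of Treatment day + 28.

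| End of Treatment | Visit 9 | Window |
|---|---|---|
| Day 15 | Day 43 | Week 4 |
| Day 29 | Day 57 | Week 8 (the target day) |
| Day 43 | Day 71 | Week 8 |
| Day 44 | Day 72 | Week 12 |
| Day 57 | Day 85 | Week 12 (the target day) |
| Day 71 | Day 99 | Week 12 |
| Day 72 | Day 100 | Week 16 |
| Day 85 | Day 113 | Week 16 |

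The listings-only default therefore reaches Visit 9 when End of Treatment is on Day 72 or later, give or take the ±3-day window. Before that, the value falls in an on-treatment window. For an early termination on Day 57, the termination visit is in the Week 8 window and Visit 9 sits exactly on the Week 12 target, with no other scheduled visit to compete for that slot.

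**Step 2: what the adverse-event rule covers.** For a last dose on Day 85, onset must be before 85 + 28 = Day 113. Most of the off-drug interval is covered. An abnormality first found at a Day 113 visit is not.

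**Step 3: the date of Visit 9.** The plan's convention is Week 12 = 12 × 7 + 1 = Day 85, so Week 16 = 16 × 7 + 1 = Day 113. That agrees with 85 + 28 = 113. The heading of Protocol 6.3.1, however, pairs Week 16 with Day 120, which is 120 − 85 = 35 days after the last dose. A cut-off of last dose + 28 + 3 days ends on Day 116 and would miss a visit on Day 120 ± 3 (Days 117 to 123). In addition, Protocol 6.4 allows the End of Treatment visit up to 7 days after the last dose, so Visit 9 can be 7 + 28 + 3 = 38 days after it.

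**Step 4: how much a follow-up table could show.** The documents do not say how many subjects will have Visit 9. Assume 5% to 30% of each arm:
- 5%: 150 × 0.05 ≈ 8 per active arm and 75 × 0.05 ≈ 4 on placebo. The 95% half-width for a mean difference is 1.96 × √(1/8 + 1/4) = 1.20 SD.
- 30%: 150 × 0.30 = 45 and 75 × 0.30 ≈ 22. The half-width is 1.96 × √(1/45 + 1/22) = 0.51 SD.

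Such a table can describe recovery but cannot support a comparison.

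**The case against.** A reader might infer that all follow-up laboratory results are barred from every table, and that recovery or late onset is never summarised by arm. The documents do not support that, for five reasons.

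- The Section 6 sentence carries an exception clause. Section 6.9.2 defers to CaPS, whose content is not in the documents, and Appendix 2 has a Week 16 row among windows used for safety data. CaPS may call for follow-up tables.
- The summary of subjects meeting monitoring and discontinuation criteria has no time limit. Its exclusion of Visit 9 follows only from the general default.
- Protocol 7.5.2 has clinically significant abnormal findings recorded as adverse events. Those starting before last dose + 28 days are tabulated by arm, so late onset is partly covered.
- Visit 9 values after an End of Treatment up to about Day 71 are not in the Week 16 window at all. Platelets reached their nadir at Week 4 in Phase 2b, so subjects stopped for platelet counts may well be among these.
- The evidence for a dose-dependent effect concerns platelets only. The protocol calls the decreases generally not clinically relevant and says mean counts rose towards baseline after Week 4.

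It can also be said that the safety objective concerns 12 weeks of treatment and that the follow-up group is self-selected.

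These points limit the size of the concern but do not close it. The CaPS reference in Appendix 2 is permissive and is not a specific note about Week 16. Adverse-event counts do not show whether values recover. The early-termination point exchanges a missing summary for mixed data.

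**Conclusion.** The point holds as a default and an inconsistency, not as an outright exclusion. As written, the SAP specifies no by-arm summary of off-drug laboratory, vital-sign or ECG values from Visit 9 when End of Treatment is on about Day 72 or later. For earlier stops it can file the same kind of value under Week 4, 8 or 12. Data of one type are thus handled in two ways according to calendar day.

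What is at stake is one of the five scheduled post-baseline on-site visits (Weeks 2, 4, 8, 12 and 16), in a subset whose size the documents do not give. No efficacy conclusion is affected. The conclusion assumes that the Section 6 default governs wherever 6.9.2 to 6.9.4 are silent. If CaPS already requires follow-up tables, the remaining work is to say so and to reconcile the windows. It is a cheap improvement.

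**What to change.** 1. In SAP Section 6, limit the listings-only sentence to efficacy data.
2. In SAP 6.9.2 to 6.9.4, add a descriptive post-treatment follow-up summary in the Safety Analysis Set, by actual treatment received as SAP 4.3 defines it. Show the value, change from baseline and change from End of Treatment. Cover at minimum platelets and the other laboratory parameters in Protocol Appendix 4 (neutrophils, lymphocytes, hemoglobin, AST/ALT, bilirubin, INR, creatinine).
3. In Appendix 2, classify safety values as on- or off-treatment by time since last dose and not by study day. State how an End of Treatment visit held some days after the last dose is classed.
4. Include Visit 9, by name and not by a 28-day cap, in the summary of subjects meeting monitoring and discontinuation criteria, labelled as post-treatment. Exclude values taken on extension-study drug.
5. Reconcile the timing of Visit 9 between Protocol 6.3.1 (Day 120/Week 16) and the Schedule of Activities (4 weeks after End of Treatment).

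The cost is some SAP wording and a few tables from data already collected. The follow-up group is a selected subset of unknown size, so the tables need a footnote saying that they are descriptive.
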